8.2 Recording of Adverse Events

At each contact with the subject, the investigator must seek information on adverse events by specific questioning and, as appropriate, by examination. Information on all adverse events should be recorded immediately in the source document, and also in the appropriate adverse event module of the case report form (CRF). All clearly related signs, symptoms, and abnormal diagnostic procedures results should be recorded in the source document, though should be grouped under one diagnosis.

All adverse events occurring during the study period must be recorded. The clinical course of each event should be followed until resolution, stabilization, or until it has been determined that the study treatment or participation is not the cause. Serious adverse events that are still ongoing at the end of the study period must be followed up to determine the final outcome. Any serious adverse event that occurs after the study period and is considered to be possibly related to the study treatment or study participation should be recorded and reported immediately.

8.3 Reporting of Serious Adverse Events and Unanticipated Problems

Investigators and the protocol sponsor must conform to the adverse event reporting timelines, formats and requirements of the various entities to which they are responsible, but at a minimum those events that must be reported are those that are:

- related to study participation,
- unexpected, and
- serious or involve risks to subjects or others (see definitions, section 8.1).

If the report is supplied as a narrative, the minimum necessary information to be provided at the time of the initial report includes:

- Study identifier
- Study Center
- Subject number
- A description of the event
- Date of onset
- Current status
- Whether study treatment was discontinued
- The reason why the event is classified as serious
- Investigator assessment of the association between the event and study treatment

8.3.1 Investigator reporting: notifying the study sponsor

Any study-related unanticipated problem posing risk of harm to subjects or others, and any type of serious adverse event, must be reported to the study sponsor by telephone within 24 hours of the event. To report such events, a Serious Adverse Event (SAE) form must be completed by the investigator and faxed to the study sponsor within 24 hours. The investigator will keep a copy of this SAE form on file at the study site. Report serious adverse events by phone and facsimile to:

Within the following 48 hours, the investigator must provide further information on the serious adverse event or the unanticipated problem in the form of a written narrative. This should include a copy of the completed Serious Adverse Event form, and any other diagnostic information that will assist the understanding of the event. Significant new information on ongoing serious adverse events should be provided promptly to the study sponsor

8.3.2 Investigator reporting:

For reportable deaths, the initial submission to the UNC IRB may be made by contacting the IRB Director or Associate Director. The AE/Unanticipated Problem Form is required as a follow up to the initial submission.

Other Reportable events:

For clinical drug trials, the following events are also reportable to the UNC IRB:

- Any adverse experience that, even without detailed analysis, represents a serious unexpected adverse event that is rare in the absence of drug exposure (such as agranulocytosis, hepatic necrosis, Stevens-Johnson syndrome).
- Any adverse event that would cause the sponsor to modify the investigators brochure, protocol or informed consent form, or would prompt other action by the IRB to assure protection of human subjects.
- Information that indicates a change to the risks or potential benefits of the research, in terms of severity or frequency. For example:
 - An interim analysis indicates that participants have a lower rate of response to treatment than initially expected.
 - Safety monitoring indicates that a particular side effect is more severe, or more frequent than initially expected.

- A paper is published from another study that shows that an arm of your research study is of no therapeutic value.
- Change in FDA safety labeling or withdrawal from marketing of a drug, device, or biologic used in a research protocol.
- Breach of confidentiality
- Change to the protocol taken without prior IRB review to eliminate apparent immediate hazard to a research participant.
- Incarceration of a participant when the research was not previously approved under Subpart C and the investigator believes it is in the best interest of the subject to remain on the study.
- Complaint of a participant when the complaint indicates unexpected risks or the complaint cannot be resolved by the research team.
- Protocol violation (meaning an accidental or unintentional deviation from the IRB approved protocol) that in the opinion of the investigator placed one or more participants at increased risk, or affects the rights or welfare of subjects.

8.3.3 Sponsor reporting: Notifying the FDA

The study sponsor is required to report certain study events in an expedited fashion to the FDA. These written notifications of adverse events are referred to as IND safety reports. The following describes the safety reporting requirements by timeline for reporting and associated type of event:

- ***Within 7 calendar days***

Any study event that is:

- associated with the use of the study drug
- unexpected,
- fatal or life-threatening, and

- ***Within 15 calendar days***

Any study event that is:

- associated with the use of the study drug,
- unexpected, and
- serious, but not fatal or life-threatening

-or-

- a previous adverse event that was not initially deemed reportable but is later found to fit the criteria for reporting (reporting within 15 calendar days from when event was deemed reportable).

Any finding from tests in laboratory animals that:

- suggest a significant risk for human subjects including reports of mutagenicity, teratogenicity, or carcinogenicity.

Additional reporting requirements

Sponsors are also required to identify in IND safety reports all previous reports concerning similar adverse events and to analyze the significance of the current event in light of the previous reports.

Reporting Process

Adverse events will be submitted on FDA Form 3500A or in a narrative format, along with FDA form 1571. If supplied as in a narrative format, the minimum information to be supplied is noted above at the beginning of section 8.3.

8.4 Stopping Rules

The study will be stopped for review if there is greater than 2 of the first 3 patients, or 5 of the first 10 patients experience an unanticipated severe adverse event, or more than one grade IV expected adverse events as defined by CTCAE v.4.0.

Study subjects will be withdrawn from the study if they experience any unknown severe adverse event (grade 3 or 4) following administration of either Ca-DTPA or Zn-DTPA. We will be using the CTCAE v.4.0 scale to measure severity of adverse events.

Any patient who shows a Grade 3 hypocalcemia (<7.0-6.0 mg/dl) post infusion therapy will be discontinued from the study.

The study will be stopped for any study-related death.

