1.4 Clinical Data to Date

Prior to formal approval by the FDA in 2005, Ca-DTPA and Zn-DTPA had been used to treat contaminated workers in the nuclear energy industry. In the period from 1958 to 1987, 485 patients received a total of 3077 doses of DTPA, about two-thirds as the calcium salt. Minor transient effects were observed in 12 patients, but no serious or long-term effects were reported. One worker was administered a total of 583 g of DTPA, primarily as the zinc salt, over a 4-year period without any observed toxicological effects (the usual recommended human dosage for a single administration is 0.5 to 1 gram).

In France, over 500 workers have been given a single dose of these agents by slow intravenous infusion and over 200 workers have received multiple dosages without adverse effects.

One of the most widely used GBCA, Magnevist, is actually a chelate of Gd and DTPA. It is estimated that 80 million doses Magnevist have been administered to patients undergoing an MRI procedure, and it has exhibited a very high safety profile. Of note, 50 million doses of Omniscan, which employs a di-amide chelator, have been administered to patients. This agent incorporates 5% free ligand in order to improve safety as it serves to scavenge Gd ions released from its chelated form. A similar di-amide Gd chelate, Optimark, contains 10% free ligand for the same reason.

DTPA is also used as a chelator for radiopharmaceuticals employing other heavy metals, e.g., ^{99m}Tc -DTPA (TechneScan®DTPA) and ^{111}In -DTPA (Pentetate Indium Disodium In 111®) used as diagnostic agents in nuclear medicine. These agents have been safely used in millions of patients over the past four decades.

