7.1 Sample Size Determination

Twenty subjects will be evaluated to determine the safety profile of chelation in this setting and to provide information on potential endpoints for future studies in this area. The distributions of urinary measures of Gd excretion as well as for pain and quality of life will be evaluated at baseline and after each treatment, as will the differences in these measures between baseline and each treatment.

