8.5 Medical Monitoring

It is the responsibility of the Principal Investigator to oversee the safety of the study at his/her site. This safety monitoring will include careful assessment and appropriate reporting of adverse events as noted above, as well as the construction and implementation of a site data and safety-monitoring plan (see section 9 Auditing, Monitoring and Inspecting). Medical monitoring will include a regular assessment of the number and type of serious adverse events.

Safety Monitoring will be performed by [name], who is not a study investigator. The CRFs and any relevant source documents will be sent to the medical safety monitor (as above) who will review them after treatment is complete for subject 1, 3, 10 and 20.

The research coordinator will complete the appropriate report form and logs; assist the PI to prepare reports and notify the IRB, FDA, and/or safety monitor of all Unanticipated Problems/SAE's.

The research coordinator and co-principal investigators will confirm that all Adverse effects (AE) are correctly entered into the AE log by the coordinator; be available to answer any questions that the coordinators may have concerning AEs; notify the IRB and FDA of all Unanticipated Problems/SAEs and AEs as appropriate. All assessments of AEs will be made by a licensed medical professional who is an investigator on the research.

Complications will be assessed by the co-PIs, categorized into major and minor categories and recorded on the CRF. CRFs and appropriate source documents will be made available to this individual for bi-monthly (every 2 months) review to ensure completeness of data collection. Any discrepancies will be immediately addressed by the co-PIs. All adverse events will be recorded and then summarized for inclusion in the final manuscript.

Data monitoring will be performed by an individual who is not a study investigator. CRFs and appropriate source documents will be made available to this individual for review to ensure completeness of data collection. Any discrepancies will be immediately addressed by the co-PIs.

- Verify receipt of all documents and supplies needed to conduct study
- Informed consent obtained for each participant
- Source document verification 100%
- CRF completion
- Investigational product accountability
- Check and review of the regulatory binder and all essential documents
- Clinical supply inventory
- SAE reporting
- Protocol amendment and their approval by the IRB

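### The count limits in 8.4 for unanticipated severe events end at patient 10 of 20, so no number of non-fatal ones in patients 11-20 requires a study-level pause

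*Combined protocol and SAP*

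**What the plan says.** Section 7.1 gives safety as a main reason for the sample size: "Twenty subjects will be evaluated to determine the safety profile of chelation in this setting".

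Section 8.4 has three triggers at study level:

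- A count of patients with unanticipated severe events: "greater than 2 of the first 3 patients, or 5 of the first 10 patients experience an unanticipated severe adverse event". The next paragraph of 8.4 ties severe to grade 3 or 4.
- More than one expected event of grade IV, with no patient window stated.
- Death: "The study will be stopped for any study-related death".

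At patient level, 4.4.1 and 8.4 withdraw a subject who has a severe event, and 8.4 discontinues a subject with grade 3 hypocalcemia.

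Section 8.5 adds oversight. The safety monitor receives the case report forms and source documents and is the person "who will review them after treatment is complete for subject 1, 3, 10 and 20". There is also this provision: "Medical monitoring will include a regular assessment of the number and type of serious adverse events". A two-monthly look at the case report forms is described as a "review to ensure completeness of data collection".

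**The concern.** The last count limit for unanticipated severe events is reached at patient 10, halfway through the planned cohort. From patient 11 on, withdrawal protects the person who had the event but does not hold back the next patient's dose.

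The triggers that do continue are oddly ordered. Two expected grade IV events among patients 11-20 stop the study for review. Ten unanticipated, non-fatal grade 3-4 events in the same patients do not. Unanticipated events are the ones a first safety study in this condition most needs to catch.

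The safety monitor's scheduled reviews do not fill the interval. After the review at subject 10, the next comes when subject 20 has finished treatment.

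A smaller wording problem sits in the same sentence. Because the phrase for exceeding a number opens the list, the second limit can be read as at least 5 or as more than 5 of the first 10.

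**Working it through.** The plan states no operating characteristics for the stopping rule, so there is no figure to reproduce.

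**Inputs**

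- Planned patients: 20 (7.1).
- Limits: 3 of the first 3 (more than 2 of 3), or 5 of the first 10, read as at least 5 (8.4).
- Event rate p: not given. Section 1.4 reports on 485 nuclear workers given these agents: "Minor transient effects were observed in 12 patients, but no serious or long-term effects were reported". That is 12/485 = 2.5% for minor effects, in a different population. I assume p from 2.5% to 40%.
- Model: independent patients with a common rate p. The rule counts patients, so each contributes at most one event. The death and expected grade IV triggers are left out.

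**Step 1: logical maximum.** With no count trigger, the first ten can contribute 4 affected patients and the second ten all 10, so 4 + 10 = 14 of 20. If the limit means more than 5, it is 5 + 10 = 15. These are bounds, not expected outcomes.

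**Step 2: chance that the rule as written acts.** The rule acts if 5 or more of the first 10 are affected, or if the first 3 are all affected with at most 1 of the next 7:

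A = P(Bin(10,p) ≥ 5) + p³ × P(Bin(7,p) ≤ 1)

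At p = 20%: A = 0.0328 + 0.008 × 0.5767 = 0.0374.

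**Step 3: late cluster that the rule ignores.** Let T = P(Bin(10,p) ≥ 5) for patients 11-20. The chance of no trigger in the first ten followed by 5 or more affected in the second ten is (1 − A) × T. At p = 20%: 0.9626 × 0.0328 = 0.0316.

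**Step 4: chance of acting if 5 or more of patients 11-20 also pauses the study.** This is A + (1 − A) × T. At p = 20%: 0.0374 + 0.0316 = 0.0690.

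| Assumed p | As written (A) | Late cluster, no pause required | With limit on patients 11-20 |
|---|---|---|---|
| 2.5% | 0.002% | 0.0002% | 0.002% |
| 5% | 0.018% | 0.006% | 0.025% |
| 10% | 0.2% | 0.2% | 0.4% |
| 20% | 3.7% | 3.2% | 6.9% |
| 30% | 15.9% | 12.6% | 28.6% |
| 40% | 37.7% | 22.9% | 60.6% |

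**Step 5: the ambiguity.** If the second limit means more than 5, A falls to 0.1%, 1.3%, 6.5% and 19.3% at 10%, 20%, 30% and 40%.

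**Step 6: an alternative.** A cumulative limit of 10 of 20, added to the present rule, acts with probability 3.8%, 17.2% and 43.1% at 20%, 30% and 40%. That is little better than the rule as written.

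**The case against.** A reader might infer that patients 11-20 are treated without safety oversight, or that 14 affected patients is a realistic prospect. The documents support neither reading.

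Several safeguards run to the end of the study:

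- Affected subjects are withdrawn, and a study-related death stops the study.
- Serious events go to the sponsor within 24 hours (8.3.1).
- The IRB must be told of new risk information (8.3.2), for example when "Safety monitoring indicates that a particular side effect is more severe, or more frequent than initially expected". This is not limited to serious events.
- IND safety reports must list previous similar events and weigh the new one against them (8.3.3).
- Under 8.5 the coordinator helps to notify the IRB, FDA and/or safety monitor of every unanticipated problem or serious event, so the monitor may hear between scheduled reviews.
- Late events in patients 1-10 still count towards the second limit while later patients are being dosed.

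Section 8.5 also calls for a site data and safety-monitoring plan. It is not among the documents and could contain further limits.

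The defence can add that this is a small feasibility study of approved agents at doses based on their package insert, that experience in nuclear workers was benign, and that several foreseeable reactions, including a symptom flare, are classed as expected and so fall outside this count. Front-loading the limits is a defensible choice.

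Most of this stands, and it lowers the weight of the point. It does not remove it. None of the routes in the protocol sets a number at which the study must pause; they leave a late cluster to judgement. Several are confined to serious events, which 8.1 distinguishes from severe ones, so a grade 3 event that is not serious can fall outside them.

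**Conclusion.** The gap is real but minor. By its text, 8.4 requires no study-level pause for any number of non-fatal unanticipated severe events in patients 11-20, and no other section of the protocol supplies a count. Whether the site safety-monitoring plan does so cannot be checked.

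The size depends on an assumed event rate. At 5% or below, the chance of an ignored late cluster of 5 or more is at most 0.006%, so the gap hardly matters. At 20% to 40% it is 3.2% to 22.9%. The gap therefore counts only if the true rate is well above what the experience in 1.4 suggests, but that is the situation for which a stopping rule is written. The probabilities rest on independent patients with a constant rate; the reading of the text does not.

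**What to change.** Reword the count clause in 8.4 to: 3 of the first 3, 5 or more of the first 10, or 5 or more of patients 11-20, with the study paused for review as soon as a limit is reached. This applies the plan's own 5-in-10 tolerance to the second half and settles whether 5 means at least 5. The largest total with no trigger falls from 14 to 4 + 4 = 8 of 20. If the site safety-monitoring plan already contains such a limit, a cross-reference would do.

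The cost is a one-sentence amendment with no new data collection. The downside is a slightly higher chance of a late pause for review: from 0.2% to 0.4% at a 10% rate and from 3.7% to 6.9% at 20%. A pause for review does not end the study.

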3.4 Primary Safety Endpoints

Clinically significant hypocalcemia will be monitored.

4 Subject Selection and Withdrawal

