4.4.1 When and How to Withdraw Subjects

Study subjects will be withdrawn from the study if they experience any known or unknown severe adverse event following administration of either Ca-DTPA or Zn-DTPA. Treatment will be discontinued immediately following any severe adverse event.

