5.5 Subject Compliance Monitoring

Subjects are treated and discharged from the clinic. They will be instructed to drink plenty of fluids, and collect urine for the following 24 hours to be returned the following day. Subjects will also have blood chemistries drawn the day following the second infusion for monitoring. Subject treatment will discontinue if they do not collect the 24 hour urine sample for testing following the infusion therapy, or refuse blood chemistry monitoring.

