8.1 Definitions

Unanticipated Problems Involving Risk to Subjects or Others

Any incident, experience, or outcome that meets all of the following criteria:

- Unexpected in nature, severity, or frequency (i.e. not described in study-related documents such as the IRB-approved protocol or consent form, the investigators brochure, etc)
- Related or possibly related to participation in the research (i.e. possibly related means there is a reasonable possibility that the incident experience, or outcome may have been caused by the procedures involved in the research,

- Serious (as defined below) “**Serious**” is different than “severe” as reported in the CTC criteria that applies a grade to the AE.

Adverse Event

An **adverse event** (AE) is any symptom, sign, illness or experience that develops or worsens in severity during the course of the study. Intercurrent illnesses or injuries should be regarded as adverse events. Abnormal results of diagnostic procedures are considered to be adverse events if the abnormality:

- results in study withdrawal
- is associated with a serious adverse event
- is associated with clinical signs or symptoms
- leads to additional treatment or to further diagnostic tests
- is considered by the investigator to be of clinical significance

Serious Adverse Event

Adverse events are classified as serious or non-serious. A **serious adverse event** is any AE that is:

- fatal
- life-threatening
- requires or prolongs hospital stay
- results in persistent or significant disability or incapacity
- a congenital anomaly or birth defect
- an important medical event

Important medical events are those that may not be immediately life threatening, but are clearly of major clinical significance. They may jeopardize the subject, and may require intervention to prevent one of the other serious outcomes noted above. For example, drug overdose or abuse, a seizure that did not result in in-patient hospitalization or intensive treatment of bronchospasm in an emergency department would typically be considered serious.

All adverse events that do not meet any of the criteria for serious should be regarded as **non-serious adverse events**.

For the purpose of this trial, the following will be considered expected adverse events:

Ca-DTPA—headache, lightheadedness, chest pain, allergic reaction, dermatitis, metallic taste, nausea and diarrhea, and injection site reactions.

Zn-DTPA—headache, lightheadedness, and pelvic pain.

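### The grade IV study stop in section 8.4 does not reliably cover hypocalcemia, the only primary safety endpoint the protocol names

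*Combined protocol and SAP*

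**What the plan says.** Section 3.4 (Primary Safety Endpoints) contains one sentence: "Clinically significant hypocalcemia will be monitored". No other safety endpoint is named.

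Section 8.1 introduces its list with "For the purpose of this trial, the following will be considered expected adverse events". It gives eight entries for Ca-DTPA, three for Zn-DTPA, and a possible flare of existing symptoms. Hypocalcemia is in none of them.

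Section 8.4 has three study-level stops:

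- Patient-window limits: more than 2 of the first 3, or 5 of the first 10, with an unanticipated severe event.
- The grade IV limit, in the same sentence: "experience an unanticipated severe adverse event, or more than one grade IV expected adverse events as defined by CTCAE v.4.0".
- Any study-related death.

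Hypocalcemia has its own sentence in 8.4, at patient level: "Any patient who shows a Grade 3 hypocalcemia (<7.0-6.0 mg/dl) post infusion therapy will be discontinued from the study". Section 4.4.1 separately withdraws a subject for "any known or unknown severe adverse event following administration of either Ca-DTPA or Zn-DTPA".

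On data and oversight, section 5.5 says "Subjects will also have blood chemistries drawn the day following the second infusion for monitoring", and section 8.5 sends the case report forms to a medical safety monitor "who will review them after treatment is complete for subject 1, 3, 10 and 20".

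**The concern.** The strictest count in 8.4, more than one event, is reserved for grade IV events that are expected. The one laboratory harm that the protocol singles out is missing from the list that 8.1 sets as expected. Two grade IV events of a listed type, such as two allergic reactions, would pause the study. Whether two patients with calcium below 6.0 mg/dl would do so depends on how the site reads one word.

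If the answer is no, the only remaining non-fatal limits need 3 of 3 or 5 of 10 patients and have nothing to act on in the second half of enrollment. The discontinuation sentence does not help at study level. It also names only the grade 3 band, so read literally it does not mention the more severe values below 6.0 mg/dl.

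**Working it through.** The plan states no error rate or operating characteristic for its stopping rules, so there is no figure to reproduce. The check has two parts.

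**1. Which limit applies to a non-fatal calcium below 6.0 mg/dl?** Section 8.4 prints the grade 3 band as <7.0-6.0, so values below 6.0 are taken as grade IV.

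| How the site classes hypocalcemia | Basis | Limit that applies |
|---|---|---|
| Expected | 8.1 treats an event as unexpected if the study documents do not describe it; the protocol does describe hypocalcemia (3.4, 8.4) | More than one grade IV event |
| Unanticipated | Not on the 8.1 list, or unexpected in severity | 3 of first 3, or 5 of first 10 |
| Anticipated but unlisted | A named endpoint with its own withdrawal rule, but not on the list | No count |

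Under the middle row, 4 of the first 10 (not including all of the first 3) plus all 10 of patients 11 to 20 could be affected without a stop: 4 + 10 = 14 of 20.

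**2. How far apart are the first two rows?**

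Inputs: N = 20 (7.1). More than 2 of the first 3 is taken as 3 of 3, and 5 of the first 10 as at least 5. The grade IV limit is taken as a stand-alone count over all 20 patients, with at most one event per patient. Only hypocalcemia is counted. Per-patient rates p are assumptions.

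For the lowest rate, section 1.4 reports on 485 treated workers: "Minor transient effects were observed in 12 patients, but no serious or long-term effects were reported". Read as 0 of 485, the one-sided 95% upper bound is 1 − 0.05^(1/485) = 0.0062, or about 0.6%. Calcium monitoring in those workers is not described, so this is weak evidence.

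More-than-one limit: P = 1 − (1−p)^20 − 20p(1−p)^19.

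- p = 0.006: 1 − 0.8866 − 0.1070 = 0.0064
- p = 0.05: 1 − 0.3585 − 0.3774 = 0.264
- p = 0.10: 1 − 0.1216 − 0.2702 = 0.608

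Patient-window limits, with q the rate of grade 3 or 4: P = q³ + P(at least 5 of 10) − q³·P(at least 2 of 7). If every case is grade IV, q = p:

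- q = 0.006: 2.2 × 10⁻⁷
- q = 0.05: 0.0002
- q = 0.10: 0.0010 + 0.0016 − 0.0001 = 0.0025

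Setting q = p gives the widest contrast, because the patient-window limits also count grade 3. Allowing for grade 3 cases, the probability that these limits do not trigger on hypocalcemia, given two or more of 20 patients below 6.0 mg/dl, is:

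| p (below 6.0) | q (grade 3 or 4) | No trigger |
|---|---|---|
| 5% | 5%, 10%, 15% | 99.9%, 99%, 97% |
| 10% | 10%, 20%, 30% | 99.6%, 94%, 79% |

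If the grade IV limit is instead tied to the first 10 patients, its trigger probabilities fall to 0.16%, 8.6% and 26.4% at p = 0.6%, 5% and 10%. No limit short of a study-related death would then act on later patients.

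**The case against.** The strongest counter-argument is textual. Section 8.4 says expected, not listed, and 8.1 ties unexpectedness to what the study documents describe. Hypocalcemia is described in the protocol, so a site could count two grade IV cases and stop. This stands. A reader might infer from the list that the grade IV limit definitely excludes hypocalcemia; the documents do not support that. They support only that the rule can be read either way.

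A reader might also infer that severe hypocalcemia is likely, or that it would go unnoticed. Neither follows. Nothing in the documents points to rates of 5% or more; the only clinical experience reported is reassuring, if weak on calcium. Patients with severe events are withdrawn under 4.4.1. Serious events go to the sponsor within 24 hours, and there are IRB and FDA reporting duties (8.3). Section 8.5 has serious events notified to the IRB, FDA and/or safety monitor and their number and type regularly assessed, in addition to the four scheduled reviews. These are real protections throughout enrollment, but none states how many cases pause dosing.

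Finally, the no-trigger percentages concern hypocalcemia alone. The patient-window limits pool all unanticipated severe events, and other stops could act first, so these figures are not the chance that the whole trial continues.

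**Conclusion.** The concern holds as an ambiguity with a real gap behind one or two of its readings. Section 8.4 does not reliably bring the named safety endpoint under its strictest study-level limit. On the list reading, hypocalcemia gets at best limits that cannot trigger after patient 10; on the anticipated-but-unlisted reading, it gets none.

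The gap in the text needs no assumed rate, but its practical size does. At 0.6% per patient, the two limits trigger with probability 0.6% and under 0.001%. At 5% it is 26% against 0.02%, and at 10% it is 61% against 0.25%, all if every case is grade IV and only hypocalcemia is counted. The higher rates are illustrations, not estimates. With individual withdrawal and reporting in place in a 20-patient, single-center feasibility study, severity is minor to moderate.

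**What to change.** Add to 8.4:

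> For the grade IV limit, hypocalcemia below 6.0 mg/dl after an infusion counts together with the listed expected events, at any point in enrollment, whether or not it is classed as expected, unless a prompt repeat test refutes it.

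In the discontinuation sentence, replace the grade 3 band with: Grade 3 or higher hypocalcemia (<7.0 mg/dl).

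Pooling matters: one grade IV hypocalcemia plus one grade IV allergic reaction would then reach the limit, which a separate hypocalcemia count would miss. The repeat-test clause fits 8.1, which already allows a repeat test to refute an abnormal value. Leave the 8.1 list unchanged, so that expedited reporting under 8.3.3 is not affected.

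The cost is two edits in one section. Calcium is already scheduled the day after each Zn-DTPA infusion (5.5; Visits 3, 7 and 11), so the only extra measurement is an occasional repeat test. The chance of a pause for review rises slightly: for hypocalcemia alone, about 0.6% over the study at a 0.6% rate, and it becomes large only if such values are common.
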